### **Safety and tolerability**

Through their extensive use in many African and South-East Asian countries, the safety and tolerability of PYR and PQP for the treatment of uncomplicated malaria when combined to AS and DHA respectively, are well established. Safety data from a European registry have also been recently published for DHA-PQP [9].

The main safety signal observed with PYR in healthy participants and malaria patients consists of transient asymptomatic AST/ALT elevations which are not associated with bilirubin changes. The most frequently reported AEs (>1/100 to <1/10) are headache, eosinophilia, neutropenia, anaemia, increased platelet count, vomiting (2.2 % to 2.5 %), abdominal pain, bradycardia, transaminase

---

increases and hypoglycaemia. Additionally, analyses performed in malaria patients suggest that no clinically concerning QTc prolongation is expected at therapeutic concentrations of PYR [10].

PQP as a combination antimalarial with DHA is well tolerated in both adults and children, with the main AEs reported being gastrointestinal disturbances such as nausea/vomiting, abdominal pain and diarrhoea [11,12]. Although transient asymptomatic ALT/AST elevations have also been described including in Phase 1 participants, these are generally mild in severity and considered as uncommon. PQP is known to induce QTc prolongation in human participants [13,14]. Despite significant hERG blockade with PQP and a mean prolongation of 15-20 msec (fasting state) demonstrated in multiple Phase 1 studies, a meta-analysis has recently concluded that patients treated with the registered three-day regimen of DHA-PQP are not at higher risk of torsades de pointes (TdP), ventricular tachycardia or other arrhythmias when compared with the normal population [15]. Based on these observations, although inducing a QTc prolongation that exceeds the ICH/FDA regulatory threshold of 10 msec, PQP is currently not considered as a torsadogenic drug provided it is taken in a fasted state and other clinical risk factors for QTc prolongation are appropriately controlled [16].

Based on the reported clinical safety profile of the two drugs, the three major toxicities of focus with combination over three days will be:

- 1) gastrointestinal toxicity (reported with both drugs)
- 2) liver toxicity (primarily expected with PYR) and
- 3) QTc prolongation (primarily expected with PQP).

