A total of four Phase 1 studies were conducted with PYR-AS in healthy participants. A SAD-MAD-Food Effect study was conducted in healthy South Korean participants [21] and three subsequent clinical pharmacology studies including a human C14 study were performed in Switzerland [22,23,24]. With the exception of the human ADME study where PYR was administered as a single oral dose, all these Phase 1 studies have evaluated the three-day therapeutic regimen of PYR-AS for acute uncomplicated malaria. Of note, the safety laboratory tests monitoring in the Asian study was limited to two post-dose time-points (72h and Day 11) while the two other studies (both DDI studies) used a very intensive monitoring with almost daily for one week and then weekly ALT/AST/bilirubin evaluations up to study end which covered a full month of observation. In the two DDI studies with ritonavir and metoprolol the LFT monitoring obtained for the control arm (i.e. PYR-AS alone) showed ALT/AST elevations with normal bilirubin consistent with the pattern described in malaria patients [22,23]. For example, in the Metoprolol DDI study, the control group of Caucasian participants dosed with PYR-AS alone over three days in Period 1 showed the following incidence of asymptomatic ALT elevations: 37 % (1-3 x ULN), 3 % (3-5 x ULN) and 10 % (>5 x ULN, including one case >20 x ULN). Similar incidences were observed for AST with 3 % of the study participants reaching values in the range 10-20 x ULN [23]. In the MAD study conducted in South Korea with four incremental doses of PYR-AS, only one case of ALT/AST elevations (>2 x ULN) was reported. However, these results should be interpreted with caution due to the very limited number of timepoints for safety laboratory tests: the study schedule did not include ALT/AST/bilirubin evaluation between Day 4 and Day 11. Additionally, a statistical comparison conducted on ALT/AST changes from baseline to Day 4 or to Day 11 in this Phase 1 study showed a statistically significant increase in ALT/AST suggesting a trend for elevation versus placebo particularly at the two highest doses of PYR 12 and 15 mg/kg [21].

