#### **8.2.5 Adverse Events of Special Interest (AESI)**

An 'AESI' is an Adverse Event of scientific or medical concern that is specific to the Sponsor or the particular product or program, for which ongoing monitoring and rapid communication by the Investigator to the Sponsor may be appropriate. It may require further investigation in order to be characterised and understood. It could be serious or non-serious and could include events that might be potential precursors or prodromes for more serious medical conditions in susceptible individuals. If an AESI is serious, reporting procedures for SAE/SUSAR will be used. For non-serious AESI, reporting procedures will be described in the SOM.

The AESIs for this protocol include, but are not limited to, the following:

- hepatic:
  - Moderate: any ALT or AST  $>3 \times$  and  $<5 \times$  ULN
  - Severe: any ALT or AST  $>3 \times$  and  $<5 \times$  ULN with symptoms/ ALT or AST  $>5 \times$  ULN with or without symptoms\*
  - Serious: ALT or AST  $>3 \times$  ULN together with an increase in bilirubin to  $>1.5 \times$  ULN
- cardiac:
  - uncorrected QT interval  $>500$  msecs, using consistent, technically valid triplicate ECG
  - second- or third-degree atrioventricular (AV) block
  - bundle branch block
  - any arrhythmia
- haematological:
  - Hb drop of  $>25\%$  from baseline on Day -1 (only for values below the laboratory reference range), or to an absolute value of  $<100$  g/L
  - platelet count drop of  $>25\%$  from baseline on Day -1 (only for values outside the laboratory reference range) or absolute value of  $<80 \times 10^9/L$ .
  - clinically significant drop from baseline in neutrophil count\*\*

\*symptoms include fatigue, nausea, vomiting, right upper quadrant pain or tenderness, fever, rash and/or eosinophilia (eosinophil percent or count above the ULN).

\*\*baseline refers to all samples taken prior to dosing on Day 1 (e.g. at screening, on Day -1).

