### **10.3 Statistical analysis of safety**

Individual participant demographics (age, gender and race) and body measurement data (height, weight and BMI) at screening will be listed. These demographic characteristics and body measurements will be summarised by treatment group and overall, using the safety analysis set. Other baseline characteristics will be listed only.

AE data will be listed and summarised using descriptive statistics: the number (and percentage) of participants who experienced any AEs and the number of AE episodes will be summarised for each treatment group. All AEs will be summarised and listed by using the System Organ Class (SOC) and Preferred Term (PT) assigned to the event using the MedDRA. Furthermore, these events will be summarised by their maximum intensity. The number of participants who experienced drug-related AEs will also be summarised. Any SAEs and/or AEs that led to trial withdrawal will be summarised and listed.

Vital signs data (SBP, DBP, HR, temperature) will be listed and summarised, along with changes from baseline, using descriptive statistics (mean, median, Standard Deviation, minimum, maximum). Out-of-reference-range values will be flagged as high or low and as being clinically relevant or not. The number of participants presenting out-of-range and clinically relevant values will be summarised.

All safety clinical laboratory data will be listed. Laboratory test results will also be compared to laboratory reference ranges. Those values outside of the applicable range will be flagged as high or low, and as clinically relevant or not. The number of participants that present out-of-range, and clinically relevant values, will be summarised. The quantitative laboratory data and changes from baseline will be summarised using descriptive statistics (mean, median, Standard Deviation, minimum, maximum). Change from baseline values at each assessment will be calculated as the assessment value minus the baseline value. The qualitative urinalysis data will be listed only.

ECG analyses will be performed on two sets of ECGs: all ECGs prior to adjudication and selected triplicates from each time-point after adjudication.

All un-adjudicated ECG data (PR, QRS, QT, QTcB, QTcF and HR) and overall ECG evaluation will be listed. ECG data and changes from baseline will be summarised using descriptive statistics (mean, median, Standard Deviation, minimum, maximum).

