### 4.11.2 Laboratory Data

Clinical laboratory parameters (including blood chemistry, haematology, coagulation, urinalysis and other laboratory results) will be listed and abnormal parameters will be flagged and graded as high (H/x) or low (L/x) (where defined) according to reference ranges and CTCAE grade. Absolute (observed) values and changes from baseline (continuous variables) will be summarized for each parameter and scheduled time point by treatment group. The number of volunteers presenting out-of-range and clinically relevant values will be summarised by treatment group. The scheduled lab value will be used for summary analysis if repeated measurements are made at any time point.

For summary statistics, a lab value with "<" will be replaced with a numeric value by removing the "<" sign. In the listings, the values will be displayed as originally reported by the laboratory.

The mean and individual change from baseline value of ALT/AST/Bilirubin will be plotted by treatment group and by time-point. The number of subjects presenting out-of-range and clinically relevant values will be summarised.

The qualitative urinalysis data will be listed only.

Test Code	Test Unit	Range Low	Range High	Grade 1	Grade 2	Grade 3	Grade 4
ALT	IU/L	10	50	>ULN - 3.0 x ULN	>3.0 - 5.0 x ULN	>5.0 - 20.0 x ULN	>20.0 x ULN

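### ALT, AST and bilirubin are graded 1 to 4 in the listings, but no planned by-arm table counts participants by worst grade, by multiple of ULN, or with transaminase and bilirubin raised together

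*SAP*

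**What the plan says.** SAP 4.11.2 states that laboratory parameters are listed and that "abnormal parameters will be flagged and graded as high (H/x) or low (L/x) (where defined) according to reference ranges and CTCAE grade". A table in the same section gives the Grade 1 to 4 limits for ALT, AST and total bilirubin. The grade is mentioned only in that sentence about listings.

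For by-arm output the section plans three things:

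- a continuous summary: "Absolute (observed) values and changes from baseline (continuous variables) will be summarized for each parameter and scheduled time point by treatment group"
- a count: "The number of volunteers presenting out-of-range and clinically relevant values will be summarised by treatment group"
- plots of mean and individual change in ALT, AST and bilirubin by arm and time point.

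Protocol 10.3 is the source of the count: "Those values outside of the applicable range will be flagged as high or low, and as clinically relevant or not". SAP 4.1 restricts summary tables to observed values from scheduled time points. SAP 4.11.2 adds that the scheduled value is used when a measurement is repeated.

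Protocol 8.2.5 defines hepatic adverse events of special interest (AESIs) in three tiers: ALT or AST between 3x and 5x ULN; the same range with symptoms, or above 5x ULN regardless of symptoms; and above 3x ULN with bilirubin above 1.5x ULN. The SAP describes no AESI table.

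**The concern.** The protocol's safety background names liver toxicity, expected mainly from PYR, among the three major toxicities of focus for the combination. The useful question is therefore how many participants in each arm reached each level of severity. Whether anyone left the reference range says less.

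The SAP already does this for another of the three. SAP 4.11.6 bands QTcF at 450, 480 and 500 ms and its change from baseline at 30 and 60 ms. For the liver, the bands are defined but no table of them is planned.

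Without such a table, the by-arm comparison of severe rises rests on an unquantified clinical judgement, on visit-wise statistics, and on whatever is recorded as an adverse event. The joint transaminase and bilirubin pattern, which in protocol Table 10 triggers a trial-level rule from a single participant, is not derived from the laboratory data in any planned summary.

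**Working it through.** **The plan's own figure.** SAP 3.2 gives the chance of at least one event in 16 participants as 1 − (1 − p)^16. At p = 0.10 this is 1 − 0.9^16 = 0.815 (stated 81%). At p = 0.20 it is 1 − 0.8^16 = 0.972 (stated 97%). Both reproduce.

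**Grade limits against AESI limits.** With the SAP's upper limits (ALT 50 IU/L, AST 37 IU/L, bilirubin 20 µmol/L):

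| | Grade 2 above | Grade 3 above | Grade 4 above |
|---|---|---|---|
| ALT | 3 × 50 = 150 | 5 × 50 = 250 | 20 × 50 = 1000 |
| AST | 3 × 37 = 111 | 5 × 37 = 185 | 20 × 37 = 740 |
| Bilirubin | 1.5 × 20 = 30 | 3 × 20 = 60 | 10 × 20 = 200 |

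The 3x and 5x transaminase limits and the 1.5x bilirubin limit of protocol 8.2.5 are therefore existing SAP grade boundaries.

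**What the out-of-range count can show.** ALT of 51 IU/L is 51/50 = 1.02 x ULN, Grade 1. ALT of 1001 IU/L is 1001/50 = 20.02 x ULN, Grade 4. Each adds one to the out-of-range count.

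**What the other outputs show.** Take two constructed sets of 16 ALT values at one visit, chosen to hold the number above ULN fixed. Set A has 8 values at 25 and 8 at 51. Set B has 8 at 25, 4 at 51, 3 at 300 and 1 at 1001.

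| | A | B |
|---|---|---|
| Out of range | 8 of 16 | 8 of 16 |
| Mean | (200 + 408)/16 = 38 | (200 + 204 + 900 + 1001)/16 = 144 |
| SD | 13 | 252 |
| Median | 38 | 38 |
| Maximum | 51 | 1001 |
| Grades 0/1/2/3/4 | 8/8/0/0/0 | 8/4/0/3/1 |

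The mean, SD and maximum react. The out-of-range count and the median do not. Only the last row gives participants per severity level, and that row is not planned.

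**Why visit-wise statistics do not supply it.** Protocol 1.2.2.2 places the PYR peak between 8 and 15 days after the first day of treatment, and the schedule samples on Days 8, 15 and 22. Participants can peak at different visits. A maximum of 300 at both Day 8 and Day 15 may be one participant or two. Protocol Table 7 allows extra safety samples. A peak found in one of these is in the listing but, under SAP 4.1, in no summary table.

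**Size at documented rates (assumption).** The protocol reports, for ALT in the group given pyronaridine-artesunate alone in the metoprolol interaction study, "37 % (1-3 x ULN), 3 % (3-5 x ULN) and 10 % (>5 x ULN, including one case >20 x ULN". Applied to 16 participants:

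- out of range: 16 × (0.37 + 0.03 + 0.10) = 8.0
- above 3x ULN: 16 × 0.13 = 2.1
- above 5x ULN: 16 × 0.10 = 1.6
- chance of at least one above 5x ULN: 81% in 16, and 1 − 0.9^8 = 57% in 8.

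**The case against.** A reader might infer that the by-arm count is merely out of range, so that a move from mild to severe rises on the combination would go unseen. The documents do not support that. The count also carries clinical relevance, and the primary laboratory endpoint concerns clinically significant change. As the constructed sets show, the continuous summary would react, and so would the individual plots. Hepatic events recorded under the tiers of protocol 8.2.5 would reach the adverse event tables of SAP 4.11.1 by severity, and the joint pattern would reach the serious-event table if reported as serious.

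Other points on that side are also fair. The cited ALT rates come from one control group of Caucasian participants who also received artesunate, whereas this trial enrols participants of Sub-Saharan African origin and gives PYR without artesunate. Elsewhere the protocol puts transaminase increases between 1/100 and 1/10. Even half of participants out of range is not saturation. With 37 participants, grades can be counted by hand from listings ordered by arm. The shell document for tables was not available, so a grade table there cannot be excluded.

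The following remains. The relevance flag is binary and has no numeric limit in the SAP, so it cannot separate Grade 2 from Grades 3 and 4. The adverse event route is uncertain: protocol 8.3 tells sites not to record separately, as adverse events, signs already captured by other protocol methods, apart from withdrawal from dosing or a symptom of another diagnosis. PYR rises are described as asymptomatic and mostly after the three dosing days. The SAP cites the shell document for page layout; what is analysed belongs in the SAP.

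**Conclusion.** The point holds as a gap in summary tables and a cheap improvement. It is not a flaw that hides a liver signal. Grades are defined and assigned, yet no table described in the SAP counts participants per arm by worst grade, above 3x or 5x ULN, or with the joint pattern.

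The grade and visit arguments rest on the documents alone. The size (about 8 of 16 out of range, about 1.6 of them above 5x ULN) is an illustration that carries over rates from another population and regimen and assumes a full combination arm. Recruitment stopped at 37, so arms may be smaller than 16 and 8. Safety is descriptive here, with no formal testing, so no error rate or power is affected. What is gained is an objective by-arm count for the primary safety objective.

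**What to change.** Keep the out-of-range and clinically relevant counts. Removing them would put the SAP at odds with protocol 10.3. Add to SAP 4.11.2 one table by treatment arm, safety set, with:

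- participants by worst post-dose grade, separately for ALT, AST and total bilirubin, using the existing grade table
- participants with ALT or AST above 3x ULN, and above 5x ULN
- participants with ALT or AST above 3x ULN together with bilirubin above 1.5x ULN, derived from the laboratory data, with a stated rule for what counts as together (for example, the same blood sample).

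State that this table includes unscheduled and repeat values, as an exception to the scheduled-only rule of SAP 4.1 and the repeat-value rule of SAP 4.11.2. The part of the severe AESI tier that depends on symptoms cannot come from laboratory values and must be taken from the adverse event data.

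The cost is one extra summary table. The values are already graded for the listings, the thresholds already stand in the documents, and no clinical rule changes.

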  - QT interval corrected using the Fridericia's formula (QTcF) >450 ms (males and females)
  - any other ECG abnormalities in the standard 12-lead ECG and 24-hour 12 lead Holter ECG or an equivalent assessment which in the opinion of the Investigator will interfere with the ECG analysis

Participants with borderline abnormalities may be included if the deviations do not pose a safety risk, and if agreed between the appointed cardiologist and the PI.

11. Has vital signs consistently outside of normal range at screening or Day -1. Acceptable normal range is as follows:
  - supine HR 40 - 100 bpm (after at least five minutes of supine rest)
  - supine blood pressure (after at least five minutes of supine rest):
    - systolic blood pressure: 90 - 140 mmHg
    - diastolic blood pressure: 40 - 90 mmHg
12. Has a positive test for Hepatitis B surface Antigen (HBsAg), Hepatitis C Antibody (HCV Ab), or Human Immunodeficiency Virus Antibody (HIV Ab) at screening

---

13. Has total bilirubin, ALT or AST consistently >ULN at screening (up to two repeats may be taken during the screening period; participant may be included if two out of the three total results are ≤ULN), or has total bilirubin, ALT or AST>ULN on Day -1 (mild variations from baseline may be allowed if considered not clinically significant by the Investigator)
14. Has a haemoglobin, platelet count, total white blood cell count, lymphocyte or monocyte count less than Lower Limit of Normal (LLN) (up to two repeats may be taken during the screening period and on Day -1 (participants may be included if two out of the three total results are greater or equal to LLN), at screening. Where there is a clear diurnal effect on the result participants may be included if variations are considered not clinically relevant by the Investigator)
15. Any other abnormal findings on vital signs, ECG, physical examination or laboratory evaluation of blood and urine samples that the Investigator judges as likely to interfere with the trial or pose an additional risk in participating
16. Positive test results for alcohol or drugs of abuse at screening or Day -1
17. Female participants who are pregnant (including a positive serum pregnancy test at screening or on Day -1) or breastfeeding
18. Male participants with a female partner(s) who is (are) pregnant or lactating at screening or on Day -1, or is (are) expected to be during the trial period

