### 2.2 Endpoints

#### Primary

- The incidence, severity and relationship of Treatment-Emergent Adverse Events (TEAEs).
- Proportion of participants with clinically significant changes in laboratory safety tests (haematology, biochemistry, coagulation and urinalysis).

- Proportion of participants with morphological and/or rhythm abnormalities on electrocardiogram (ECG).
- Proportion of participants with clinically significant changes in ECG time intervals (PR, QRS, QT and QTc intervals) and clinically significant changes against baseline Holter.
- Proportion of participants with clinically significant changes in vital signs (systolic blood pressure, diastolic blood pressure and pulse rate).

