## 4.11.3 Vital Signs

Vital signs data (SBP, DBP, Pulse rate, temperature) will be listed for individual subjects. Summary statistics of absolute (observed) values and changes from baseline will be calculated for each parameter and scheduled timepoint by treatment group.

Out-of-reference-range values will be flagged as high (H) or low (L) and as being clinically relevant or not: the number of subjects presenting out-of-range and clinically relevant values will be summarised.

Parameter	Normal Range
Temperature (tympanic)	35-37.5°C
Systolic Blood Pressure (Supine)	90-140 mmHg
Diastolic Blood Pressure (Supine)	40-90 mmHg
Postural Drop (systolic, symptomatic)	≤20 mmHg drop
Pulse Rate (supine)	40-100 bpm
Respiratory Rate	8-20 breaths per min

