# Statistical Analysis Plan

All un-adjudicated ECG data (PR, QRS, QT, QTcB, QTcF and HR) including H/L flags and overall ECG evaluation will be listed. Out-of-reference-range values will be flagged as clinically relevant or not. Reference ranges for ECGs are as follows:

Parameter	Normal Range
Heart Rate (Supine)	40-100 bpm
PR Interval	120-220 ms
QRS duration	≤120 ms
QTcF	≤450 ms (Males & Females)

For summary statistics an arithmetic mean value, of the last 3 evaluable ECGs of each timepoint, will be used at each time-point. All below analyses will be performed using this set.

ECG data and changes from baseline will be summarised using descriptive statistics.

The change from baseline will be derived using the arithmetic mean value of each time-point triplicate minus baseline value, where baseline is the arithmetic mean of the pre-dose QTcF values of Day 1.

Furthermore, categorical analysis of QTcF data will be presented as follows:

- Absolute QTcF interval prolongation
  - QTcF interval > 450 ms to ≤ 480 ms
  - QTcF interval > 480 ms to ≤ 500 ms
  - QTcF interval > 500 ms
- Change from baseline in QTcF interval
  - QTcF interval increases from baseline > 30 msec to ≤ 60 msec
  - QTcF interval increases from baseline > 60 ms

The mean change from baseline value of QTcF will be plotted by treatment group and by time-point. The number of subjects presenting out-of-range and clinically relevant values will be summarised.

Additional categorical analysis will be presented as follows:

- increase of PR from baseline >25% resulting in PR > 200 ms
- increase of QRS from baseline >25% resulting in QRS > 120 ms
- decrease of HR from baseline >25% resulting in HR < 50 bpm
- increase of HR from baseline >25% resulting in HR > 100 bpm.

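### The by-arm laboratory and vital-sign counts have no post-dose or baseline condition, although the primary endpoints they report are changes; participants abnormal before dosing can be counted as cases

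*SAP*

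**What the plan says.** SAP 2.2 (and Protocol 2.2.1) words three of the primary endpoints as changes:

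- laboratory: "Proportion of participants with clinically significant changes in laboratory safety tests (haematology, biochemistry, coagulation and urinalysis";
- vital signs: "Proportion of participants with clinically significant changes in vital signs (systolic blood pressure, diastolic blood pressure and pulse rate";
- ECG intervals: "Proportion of participants with clinically significant changes in ECG time intervals".

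A fourth is worded as presence, not change: "Proportion of participants with morphological and/or rhythm abnormalities on electrocardiogram (ECG".

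The participant-level counts planned for them are:

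- SAP 4.11.2: "The number of volunteers presenting out-of-range and clinically relevant values will be summarised by treatment group";
- SAP 4.11.3: "the number of subjects presenting out-of-range and clinically relevant values will be summarised";
- SAP 4.11.6: "The number of subjects presenting out-of-range and clinically relevant values will be summarised".

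SAP 4.1 builds summary tables from observed values at scheduled time points. It defines baseline, unless otherwise stated, as the last non-missing value before first dosing, and uses it for change scores. Protocol Table 5 schedules laboratory tests, vital signs and ECGs at screening and Day -1 as well as after dosing.

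SAP 4.11.6 also plans ECG categories that do use baseline: QTcF increases of more than 30 and more than 60 ms, and changes above 25% in PR, QRS or HR that cross an absolute limit. Continuous changes from baseline are summarised in all three domains, and individual ALT, AST and bilirubin changes are plotted.

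**The concern.** The endpoint is a change and the count is a state. For laboratory and vital signs no other participant-level table measures change, and mean changes do not give a proportion of participants. Elsewhere the documents do supply the missing condition: a TEAE must start after dosing (SAP 4.11.1), the haemoglobin, platelet and neutrophil events of special interest are drops from baseline (Protocol 8.2.5), and several ECG categories refer to baseline.

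Entry rules let pre-dose abnormality through. Exclusion 14 reads "Has a haemoglobin, platelet count, total white blood cell count, lymphocyte or monocyte count less than Lower Limit of Normal (LLN" and does not name neutrophils, although the protocol lists neutropenia among the frequent PYR events. Exclusion 13 tolerates mild Day -1 variation in liver tests. Exclusion 11 removes only vital signs that are consistently out of range.

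Randomisation balances such participants only on average. In arms of 8 and 16, one or two more of them in one arm is as large as a plausible drug signal, and could imitate or hide one.

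**Working it through.** **1. The plan's own figure.** SAP 3.2 gives the chance of at least one case among 16 on the combination as 81% at a 10% event rate and 97% at 20%. Both reproduce: 1 - 0.90^16 = 0.815 and 1 - 0.80^16 = 0.972.

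**2. What pre-dose cases would do to it.** The documents give no pre-dose abnormality rate. Let q be the assumed share of participants counted, per parameter, on a pre-dose value. The chance of at least one such case in an arm of n is 1 - (1 - q)^n. With a true new-onset rate of 10%, independent of q, the apparent rate is 1 - 0.90(1 - q).

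| q | at least 1 in 8 | at least 1 in 16 | apparent rate |
|---|---|---|---|
| 1% | 8% | 15% | 10.9% |
| 2.5% | 18% | 33% | 12.3% |
| 5% | 34% | 56% | 14.5% |
| 10% | 57% | 81% | 19.0% |

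At q = 10% the arm of 16 shows a case 81% of the time with no drug effect at all, the same probability the plan quotes for a genuine 10% event.

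**3. Repeated visits.** Protocol Table 5 gives full blood panels at screening, Day -1 and Day 1 (taken here as pre-dose, so 3 pre-dose). After dosing they fall on Days 4, 5, 6, 8, 15, 22 and 30, with Day 7 for the sentinel group, so m = 7 or 8. Assume each participant has a stable normal component b with visit-to-visit correlation r, no drug effect, and p(b) the chance of being out of range at one visit. Averaging over b:

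- counted over all visits: A = mean of 1 - (1 - p)^(3+m);
- in range at the last pre-dose value and out of range after dosing: B = mean of (1 - p)[1 - (1 - p)^m].

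For a lower limit z, p(b) = Φ((z - b√r)/√(1 - r)); a two-sided interval adds the upper tail. Ranges below cover m = 7 to 8, as shares of all participants.

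| Assumed parameter | A | B | A - B (points) |
|---|---|---|---|
| 10% below limit per visit, r = 0.7 | 31-32% | 19-20% | 12 |
| 25% below limit per visit, r = 0.7 | 57-58% | 29-31% | 28 |
| 95% interval, r = 0.5 | 29-30% | 20-22% | 8-9 |
| 95% interval, r = 0.7 | 21-22% | 14-15% | 7 |
| 95% interval, r = 0.85 | 15-16% | 9-10% | 6 |

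In an arm of 8 the first two rows mean 8 × 0.31 = 2.5 to 8 × 0.58 = 4.6 counted, against 8 × 0.19 = 1.5 to 8 × 0.31 = 2.5. For the ordinary interval the gap is 8 × 0.06 to 8 × 0.09, or about 0.5 to 0.7 of a participant.

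**4. What these figures cover.** They describe an out-of-range count with no entry screening modelled. If clinical relevance is also required they are upper bounds. B counts only new abnormalities; worsened ones would be added. The false counts left in B come from repeated post-dose visits, and the fix does not remove them.

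**The case against.** **The counts are not of any out-of-range value.** They also name clinical relevance, and the protocol and SAP flag each out-of-range value as clinically relevant or not. This stands. But it is unclear whether the two conditions are joint: the commas in Protocol 10.3 suggest two separate counts. The plan also never says that the flag is judged against baseline.

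**The ECG section does refer to baseline.** A reader might infer that the ECG tables carry no such condition. That is wrong. Only the out-of-range count and the absolute QTcF categories lack one, and the morphology and rhythm endpoint is not worded as a change.

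**The SAP does not say that pre-dose abnormality counts.** This stands: it can count, because the text is silent. Nor does the SAP say whether the count is per time point or over the study. A per-time-point layout would keep pre-dose values out of the post-dose rows, but not participants whose abnormality simply persists.

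**Entry and safety rules limit the problem.** Inclusion 6 and exclusion 15 screen for clinically significant findings, relevant pre-dose results go to medical history (Protocol 7.1), and a clinically significant neutrophil drop is an event of special interest. These reduce the number of clinically relevant pre-dose cases. None of them takes a value out of the counts.

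**The trial is exploratory, the safety analysis is descriptive, and all values are listed.** This bears on how serious the point is, not on whether the table matches its endpoint.

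Two larger figures are tempting. With 39 repeat blood parameters, 1 - 0.95^39 = 0.865 suggests that about 86% of participants are abnormal on something at one visit. But no pooled count is planned, the tests are plainly dependent (urea and BUN, the bilirubin fractions), and the figure is the same before and after dosing. Requiring normality at every pre-dose visit would lower the 19-31% to about 12-18%, but SAP 4.1 defines baseline as the last pre-dose value.

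**Conclusion.** The point holds for the laboratory and vital-sign counts, and for the out-of-range count and absolute QTcF categories in SAP 4.11.6. The planned laboratory and vital-sign counts do not measure the primary endpoints as worded, and they permit participants abnormal before dosing to be counted as cases. The documents do not support saying that every out-of-range value counts, that such participants certainly will be counted, or that the ECG plan ignores baseline.

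The size depends on assumed rates and correlations, not trial data. It is about 12 to 28 points per parameter where 10-25% are abnormal at any visit, and about 6 to 9 points for an ordinary 95% reference interval. Counts are smaller if clinical relevance is a joint condition. Recruitment stopped at 37, so some arms are a little smaller than planned. This should be changed because the tables report primary endpoints in very small arms; it does not invalidate the trial.

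**What to change.** In SAP 4.11.2, 4.11.3 and the out-of-range count of 4.11.6:

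1. Count only post-dose values.
2. Define a case as new (in range at baseline, out of range after dosing) or worsened from baseline, by at least one grade where grades are defined. Use the SAP 4.1 baseline for laboratory and vital signs, and the Day 1 pre-dose mean of 4.11.6 for ECG.
3. State whether out-of-range and clinically relevant form one joint count or two, and whether the count is per time point or over the study.
4. Add a baseline-to-worst-post-dose shift table by arm. Grades for ALT, AST and bilirubin are already set out in 4.11.2.

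The existing baseline-referenced ECG categories can stay as they are. No new data are needed. The cost is SAP wording, some extra programming and smaller counts.
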